B. Statistical Considerations

B.1. Sample Size Justification:

Our sample sizes were chosen based on an iterative process involving determining the size of the target population eligible, feasibility constraints, and then verifying adequate power to test the hypotheses across all of our proposed studies for Projects 1-5. Through these detailed considerations, and input from our expert statisticians, we have been able to verify adequate power to address all of our study aims with the proposed sample sizes for the SAGES I SELECT subsample (N=148), the SAGES II cohort (N=460) and the SAGES II subsample (N=180). Power has similarly been verified for all aims of each project. For SAGES II, approximately 50% of the cohort will be enrolled at BIDMC and 50% at BWH. The data, however, will be analyzed together. Computations allow for two-sided type-I error probability 0.05 and to take into account cumulative attrition consistent with our experience in this population. We use multiple imputation to account for missing data where appropriate.

B.1.2. Experimental design and sampling: general considerations

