Aim 1. To prospectively examine in a new cohort of 400 patients (SAGES II) enriched with MCI, the relationship between baseline CSF AD biomarkers (i.e., CSF A β 42, t-tau, p-tau, tau/A β 42 ratios, and neurofilament light (NFL)), sampled prior to spinal anesthesia and (1) development of post-operative delirium; and (2) cognitive decline over 18-36 months following delirium. Sample size and statistical power considerations. Hypothesis 1A: The first part of this compound hypothesis statement can be simplified to detecting a mean difference on the random effect (individually-varying slope) across biomarker groups. A two-group mean comparison will allow for the detection of effect sizes from d = 0.28 to 0.33 standardized units (i.e., standardized mean difference between groups) when biomarker positivity ranges from 25% to 50% (as above). These minimum detectable effect sizes are smaller than those demonstrated in SAGES I for the effect of delirium in the long-term cognitive slope, which was d = 0.48 standardized units,²² and feasible based on effect sizes from our MSD approach.⁵⁶ Hypothesis 1B: The second component requires only that the effect of delirium and biomarker positivity not be completely confounded in predicting cognitive slope, which is highly unlikely. Thus, we are confident that we have adequate power to test this Aim.

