Aim 2. To evaluate associations of delirium and CSF AD biomarkers (sampled near 4 year follow-up) in a probability sample from SAGES I (N=128): (1) 64 patients who developed delirium during the initial hospitalization; (2) 64 who did not develop delirium during initial or subsequent hospitalizations. Statistical power and sample size considerations. Hypothesis 2a: The analytic question can be simplified as detecting a difference on a continuous dependent variable--the individually varying time slope--across delirium and non-delirium groups. With two groups of size 64, Lehr's equation⁵⁷ informs that with assumptions of 5% and 20% type-I and type-II error rates, the minimum detectable effect size is d = 0.5 standardized units. This is close to the observed effect we have reported out to 3 years in our parent study cohort (d = 0.48),²² and feasible to detect with our MSD approach.⁵⁶ Hypothesis 2b: Since we expect to find stronger effects with longer follow-up from this analysis, we anticipate adequate power to address this hypothesis. Utilizing a two-sample t-test for the difference in slopes across biomarker groups results in a minimal detectable effect size of d= 0.53, with an overall positivity rate of 34% (30% in 109 cognitively normal and 60% in 19 with MCI), which should be feasible to detect based on our prior studies. Hypothesis 2c: Since purely descriptive, power is not calculated.

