Aim 1 Analyses: Aim 1 proposes to evaluate the relationship between baseline CSF AD biomarkers (CSF A $\beta_{42/40}$; t-tau; p-tau, tau/A β ratios, and NFL) and (1) the development of post-operative delirium; and (2) the pace of cognitive decline over 18-36 months following delirium. Hypothesis 1a posits that patients with abnormal CSF AD biomarker levels at baseline will have an increased risk of delirium following surgery, compared to patients with normal biomarker levels. This aim will be tested in the SAGES II cohort (N=460) with logistic regression models, with the occurrence of delirium as the outcome and biomarker positivity (abnormal level) as the main exposure variable. Control variables will include age, gender, nonwhite race, education, Charlson score, depression, impairment in any instrumental activity of daily living, surgery type, IQCODE, and baseline GCP score. To avoid overcontrolling for variables that might be intermediaries between delirium and its effect on cognitive trajectory,^{70,71} we will not adjust for hospital-related factors. Missing data will be addressed using multiple imputation (50 imputations) and the chained equations approach.⁷² Hypothesis 1b is a compound hypothesis statement that requires testing of 2 sub-hypotheses: (1) patients with abnormal CSF AD biomarker levels at baseline will have an increased risk for cognitive decline compared to those with normal biomarker levels, (2) the greatest decline will be observed in those with delirium and abnormal biomarker levels. This hypothesis will be tested with a generalized linear mixed effect modeling framework with a piecewise time basis describing the course of cognitive change by 3 timeperiods (acute period: pre-operative to 1 month; recovery period: 1-2 months; and long-term trajectory: >2-36 months), as we have done previously.^{22,26,63} The dependent variable is the GCP composite.^{55,73} The first part of this hypothesis, that biomarker positivity is related to cognitive decline, will be tested by regressing repeatedly observed cognition on time, biomarker positivity, and their interaction (with pre-specified control variables as described above). The hypothesis that biomarker positivity is associated with faster long-term decline is evaluated with the interaction of biomarker positivity and the long-term time trend. The second part of this hypothesis (the group with delirium and biomarker

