positivity has the steepest slope) requires that in addition to biomarker positivity being related to slope, delirium must be related to slope (as shown previously)²² and that the two effects are at least partially independent (i.e., the effect of biomarker positivity is only partially mediated by delirium). Aim 2 Analyses: The goal of Aim 2 is to evaluate associations of delirium and CSF or PET AD biomarkers sampled near 4 year follow-up among delirium cases and controls (n=74 each group). Control variables will include age, gender, race, education, Charlson, depression, functional impairment, surgery type, IQCODE, and baseline GCP score. Missing data will be handled using multiple imputation (50 imputations) and the chained equations approach.⁷² Hypothesis 2a. This hypothesis will be evaluated using generalized linear mixed effect modeling as described above for H1b, applying an approach similar to what we have used in our prior publications.²² The outcome is the composite measure, GCP, 55,73 and the main exposures are delirium group, time, and their interaction. A faster rate of LTCD among those with delirium is demonstrated by a significant interaction term for delirium group by long-term time trend. Hypothesis 2b. This hypothesis will be tested with generalized linear effects models as in H2a with biomarker positivity as the primary exposure, rather than delirium. We assume higher rates of biomarker positivity than in Aim 1, since 50% will have delirium and the overall group will have higher rates of cognitive impairment by frequency matching.

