Aim 3 Analyses: Hypothesis 3a posits that CSF and plasma t-tau and NFL will have Pearson correlation of at least r = .50. This analysis will be approached with correlational methods. Variables will be evaluated and transformed as appropriate prior to estimating a correlation coefficient. Hypothesis 3b seeks to test if abnormal levels of t-tau and NFL from stored plasma at baseline will be associated with a higher risk of developing delirium and greater delirium severity. This will be tested with logistic regression (delirium occurrence) and linear regression (delirium severity). The control variables will be the same as above. Missing data will be addressed using multiple imputation (50 imputations) and the chained equations approach.⁷² Hypothesis 3c seeks to test if patients with abnormal levels of t-tau and NFL from stored plasma at baseline will have a faster rate of LTCD (over a minimum of 8 years) compared to those without abnormal biomarker levels. This hypothesis will be evaluated using generalized linear mixed effect modeling as described above for H1b and as previously conducted in our prior publications.²² The outcome is a composite measure of cognitive functioning^{55,73} and the main exposures are biomarker abnormality, time and their interaction. A faster rate of LTCD among those with delirium is revealed by a significant interaction between delirium group and the long-term time trend. Hypothesis 2c. The analytic approach is similar to H1b, and posits that the two effects are at least partially independent in the generalized linear effects models (i.e., the effect of biomarker positivity is only partially mediated by delirium). Since purely descriptive, power is not calculated.

Project 2

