Aim 3 Analysis: For H3A, the analytic strategy will be similar to that described in Aim 1 with measured levels of inflammatory proteins (and the inflammatory index) being the independent variables, and delirium and LTCD being the outcomes. We will examine plasma markers at PREOP, POD2, and LTFU, and CSF at one time point, LTFU. We anticipate seeing the lowest levels of inflammatory markers in the group without delirium and slow rates of LTCD, and the highest levels in those with delirium and faster rates of LTCD. We will perform multivariable analyses using generalized linear models with a log link for delirium incidence, and identity link for continuous LTCD. In H3B, to examine interactions with CSF AD biomarkers, we will select the most predictive inflammatory (IL-6, CRP, sTNFR1, or the inflammatory index) and AD biomarker (A β_{42} , t-tau, p-tau, or p-tau/A β_{42} ratio) and put both into the generalized linear model together. We expect significant independent effects of both inflammatory markers and CSF AD biomarkers on delirium and LTCD.

Project 3

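### Three stated tests do not match their hypotheses: Project 1 H3c reads the wrong interaction, Project 2 H3B has no interaction term, and Project 1 H1b(2) is inferred from untested additivity

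*Protocol*

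**What the plan says.** **Project 1, H1b(2).** B.2.3 (Aim 1 Analyses) splits H1b into two sub-hypotheses. The first, biomarker positivity and decline, is matched to its proper term, biomarker by long-term time. The second is that "the greatest decline will be observed in those with delirium and abnormal biomarker levels". For this the plan "requires that in addition to biomarker positivity being related to slope, delirium must be related to slope (as shown previously"), and it asks that the two effects be at least partially independent. It names no biomarker x delirium x time term and no contrast of the double-positive group with either single-positive group. The power text in B.1.3, where the same question is labelled 1B, says "The second component requires only that the effect of delirium and biomarker positivity not be completely confounded in predicting cognitive slope" and gives no calculation.

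**Project 1, H3c.** B.2.3 (Aim 3 Analyses) asks whether abnormal plasma t-tau and NFL at baseline go with faster long-term decline. The listed exposures are biomarker abnormality, time and their interaction. The decision sentence then says: "A faster rate of LTCD among those with delirium is revealed by a significant interaction between delirium group and the long-term time trend".

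**Project 2, H3B.** B.2.3 (Aim 3 Analysis) begins: "In H3B, to examine interactions with CSF AD biomarkers, we will select the most predictive inflammatory" marker out of four (IL-6, CRP, sTNFR1, the inflammatory index). It likewise takes the most predictive of four AD markers. Both then enter one generalized linear model, and the expected finding is independent effects of each. No product term is named, and no correction for the selection.

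**The concern.** Each rule can return a positive answer for a reason other than its hypothesis.

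- **H3c:** a delirium effect on slope, which the programme already expects, would be read as support for a plasma biomarker.
- **H3B:** two main effects would be reported where an interaction was asked for. The nominal p-values of markers chosen as the strongest on the same patients would be too small.
- **H1b(2):** two separate effects on slope would be taken to show that patients with both features decline most, even if having both is no worse than having one. Whether delirium and AD pathology add up is a central question of the programme.

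**Working it through.** **The plan's own figure.** Inputs: "Computations allow for two-sided type-I error probability 0.05" (B.1); "assumptions of 5% and 20% type-I and type-II error rates" (stated for Project 1 Aim 2); "To prospectively examine in a new cohort of 400 patients (SAGES II) enriched with MCI" (B.1.3, Project 1 Aim 1); positivity 25-50%. With MDE = 2.80 x sqrt(1/n1 + 1/n2):

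- 50% positive: 2.80 x sqrt(1/200 + 1/200) = 0.28
- 25% positive: 2.80 x sqrt(1/100 + 1/300) = 0.32 (0.33 by Lehr's form)

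The stated 0.28-0.33 reproduces. It covers a single two-group effect on slope, not the joint claim.

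**H3c.** Take no biomarker effect and the SAGES I delirium effect, d = 0.48 (B.1.3). The chance that delirium by time is significant is Phi(d x sqrt(n/2) - 1.96):

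- 64 per group: 0.48 x sqrt(32) = 2.72, giving about 0.77
- 74 per group: 0.48 x sqrt(37) = 2.92, giving about 0.83

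**H3B.** With four independent null markers, the chance that the best is nominally significant is 1 - 0.95^4 = 0.186. The documents give no between-marker correlations, so these are assumed:

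| Correlation | Type I error per class |
|---|---|
| 0 | 19% |
| 0.5 | about 15-16% |
| 0.8 | 11% |
| 0.9 | 9% |

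**H1b(2).** Positivity is 25-50% (Project 1 Aim 1). Delirium is 24% in biomarker-negatives and 24-36% in positives; the 24% is the SAGES II figure used for Project 4 Aim 3a, and the 36% comes from the Project 3 power text. Slopes have unit SD and data are complete. Suppose biomarker-only, delirium-only and double-positive patients all decline by d = 0.48, so having both is no worse. Simulated chance that both mutually adjusted effects are significant and adverse:

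| N | 25% positive, 24% delirium in positives | 50% positive, 36% delirium in positives |
|---|---|---|
| 400 | 75% | 43% |
| 460 | 83% | 50% |

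Requiring double-positive to be significantly worse than each single-positive group gives about 1% or less.

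If the effects are truly additive at 0.48 each (N=400, 24% delirium in both biomarker groups), the plan's rule succeeds in 97-98% of studies and the two contrasts together in 42-60%.

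**Detectable differences at N=460.** At 25% positive and 24% delirium throughout, the cells are 27.6 (both), 87.4 (biomarker only), 82.8 (delirium only) and 262.2 (neither):

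- v biomarker-only: 2.80 x sqrt(1/27.6 + 1/87.4) = 0.61
- v delirium-only: 2.80 x sqrt(1/27.6 + 1/82.8) = 0.62
- three-way term: 2.80 x sqrt(1/27.6 + 1/87.4 + 1/82.8 + 1/262.2) = 0.71

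At 50% positive and 36% delirium in positives (cells 82.8, 147.2, 55.2, 174.8) the same formulas give 0.38, 0.49 and 0.58.

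**The case against.** **H1b(2) is an ordering claim, not a claim of synergy.** This stands. If effects on slope are additive, two adverse independent effects do imply that the double-positive group declines most. The false-support figures also depend on the scenario: they assume full saturation at d = 0.48 and would be lower for smaller effects.

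**A reader might infer that H1b(2) cannot fail.** The documents do not support that. The rule needs both effects, and with one truly null it is met in only about 2-3% of studies.

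**Interactions are not excluded.** B.2.1 allows interaction terms as appropriate for covariates, and B.2.2 refers to project proposals for detail. But B.2.3 says what H1b(2) requires, and neither a joint term nor a group contrast is in it. Elsewhere the protocol does name modification by delirium (Project 3 H1b, Project 4 Aim 2c).

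**H3c looks like a misplaced sentence.** It nearly repeats the H2a wording, the listed exposures include the right term, and the power text in B.1.3 compares biomarker abnormal with normal. A reader might conclude that the study will test the wrong exposure. The text shows only a contradiction between model and decision sentence.

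**H2c might seem to share the fault.** It does not. It is labelled purely descriptive and posits only partial independence, which mutually adjusted effects address. The SAGES II detectable differences would not apply to it either, since it concerns the SAGES I SELECT sample.

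**Conclusion.** The point holds for three tests.

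- **H3c:** the decision sentence contradicts the hypothesis and the listed model. Followed literally, it gives a positive reading with probability about 0.77-0.83 when the biomarker has no effect and delirium has d = 0.48.
- **H3B:** an interaction is announced and no product term is specified. Selecting each marker as best of four, with no correction stated, puts type I error at about 9-19% per class for correlations from 0.9 down to 0.
- **H1b(2):** the ordering is inferred, and the inference depends on additivity that is not checked. If having both features is no worse than having one, false support arises in about 43-75% of studies at N=400 and 50-83% at N=460, on the positivity, delirium and unit-SD assumptions above. Under additivity the inference is right.

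These are mismatches in tests that the protocol itself states, not detail left to a later plan.

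**What to change.** - **H3c:** replace the decision sentence so that the hypothesis is judged on biomarker abnormality by long-term time. This is a one-line correction.
- **H3B:** add the inflammatory x AD-biomarker product term, or reword the hypothesis as independent effects. Either pre-specify the marker pair or obtain p-values that repeat the selection step, for example by permutation.
- **H1b(2):** fit biomarker x time, delirium x time and biomarker x delirium x time together, using the long-term segment. Base the hypothesis on double-positive v biomarker-only and double-positive v delirium-only, both required, with confidence intervals. State the detectable differences at N=460: about 0.38-0.61, 0.49-0.62, and 0.58-0.71 for the three-way term. Attrition would enlarge them.

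The cost is a few model terms and contrasts on data already planned, plus honest imprecision. With delirium at 24% in both biomarker groups, the three-way term needs 1/sqrt(0.24 x 0.76) = 2.3 times the effect detectable for biomarker positivity alone. Power for the two contrasts is also well below that of the present rule when effects are additive.

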Aim 3. To examine the relationship of novel SiMoA assays of t-tau and NFL in plasma obtained prior to surgery in SAGES I (n=148) with delirium incidence/severity and LTCD following delirium. Sample size and statistical power considerations. Hypothesis 3a: With a sample size of 148, the minimum detectable correlation coefficient is r = .25 (using single sample two-sided type-I error level of 5% and type-II error level of 20%). A single sample, one-sided test that the observed correlation is greater than r = .50 is associated with 5% type-I error and 80% power. Given our pilot yielding r=.61 and the literature r=0.52-0.89,^{58,59} we anticipate adequate power. Hypothesis 3b: Here we assume similar rates of biomarker positivity as in Aim 2. Given a minimum detectable rate ratio of exp(4/sqrt(n)), where n is the harmonic mean of the sample with and without abnormal levels of t-tau and NFL⁶⁰ and levels of type-I and type-II error of 5% and 20%, respectively, as biomarker positivity ranges from 30 to 60%, our minimum detectable odds ratio for the association of biomarker positivity and delirium will range from 2.8 to 3.7, describing areas under the ROC curve (AUC) of 0.62 to 0.66, which are medium to large effects.⁶¹ For delirium severity, the minimum detectable effect size varies from d = 0.50 to 0.55 as biomarker positivity ranges from 30 to 60%. These effects are feasible to detect given prior work showing A β_{42} and tau positivity rates of 70-80% in delirium vs. 40-50% in nondelirium, and odds ratios for delirium given biomarker positivity of 2.1-3.2.62 Hypothesis 3c: The analytic question can be simplified as detecting a difference on a continuous dependent variable -- the individually varying time slope--across biomarker abnormal vs. normal groups. With a balanced

distribution of biomarker abnormality and with two groups of size 64, Lehr's equation⁵⁷ assuming 5% and 20% type-I and type-II error rates, yields a minimum detectable effect size ranging from d = 0.50 to 0.55 standardized units as biomarker positivity ranges from 30% and 60%. These effects appear feasible to detect given our prior studies and the published literature.^{22,62}

Project 2

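### Project 1 Aim 3 states its aim in plasma levels but tests H3c, and by its wording H3b, on abnormal v normal; if the effect is linear this gives up about 14–23 points of power at the 80% design point.

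*Protocol*

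**What the plan says.** - **Aim.** Protocol A.2.1 describes Aim 3 as relating the pre-operative levels of plasma t-tau and NFL to delirium incidence, delirium severity and LTCD. Table 1 labels the aim exploratory.
- **H3a** (B.2.3, Project 1, Aim 3 Analyses) correlates CSF with plasma values as continuous variables, transformed if needed.
- **H3b** (same section) is put in terms of abnormality: "Hypothesis 3b seeks to test if abnormal levels of t-tau and NFL from stored plasma at baseline will be associated with a higher risk". The models are logistic regression for occurrence and linear regression for severity. The sentence naming the models does not state how the exposure is coded.
- **H3c** (same section) is explicit: "the main exposures are biomarker abnormality, time and their interaction".
- **Power** (B.1.3, Project 1, Aim 3) treats both hypotheses as a comparison of biomarker-positive with biomarker-negative patients: "Here we assume similar rates of biomarker positivity as in Aim 2". Positivity is varied from 30% to 60%. The stated detectable effects are d = 0.50–0.55 for severity and LTCD, and an odds ratio of 2.8–3.7 for delirium. The same section cites odds ratios of 2.1–3.2 from prior work as support for feasibility.
- The protocol gives no plasma cut-point, and no analysis of H3b or H3c on the continuous level.

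**The concern.** The aim is about levels and the assay returns levels, but the planned contrast uses only the side of a cut on which a patient falls. The positivity rate in the power text is borrowed from Aim 2, where status comes from CSF or PET, so it is not tied to any plasma threshold. Elsewhere the protocol uses marker values directly. Project 2 Aim 3 enters measured inflammatory levels as predictors in the same 148 patients, and Project 5 Aim 1 is powered per half-SD of a continuous marker.

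At stake is power in a sample that cannot grow. Most of the 2.1–3.2 range cited for feasibility lies below the 2.8–3.7 that the protocol says the binary contrast can detect. A null binary result could therefore close off a marker whose measured level would have shown an association.

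**Working it through.** **Inputs from the protocol**
- Error rates: "levels of type-I and type-II error of 5% and 20%, respectively"; and, in B.1, "Computations allow for two-sided type-I error probability 0.05".
- Sample for Aim 3: "in plasma obtained prior to surgery in SAGES I (n=148"). The H3c figure instead rests on a balanced "distribution of biomarker abnormality and with two groups of size 64", that is N = 128.
- Delirium split: "among delirium cases and controls (n=74 each group").
- Positivity q = 30–60%.

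**Assumptions not in the protocol.** The transformed level is normal, and its relation to the outcome is linear (log-odds linear for delirium). There is no covariate adjustment.

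**1. Reproduce the stated d.** Lehr's rule is d = 4/√h, with h = 2Nq(1−q), the harmonic mean of the group sizes.
- N = 128: q = 0.30 gives h = 53.76, d = 0.546; q = 0.50 gives h = 64, d = 0.500; q = 0.60 gives h = 61.44, d = 0.510. This matches 0.50–0.55.
- N = 148: h = 62.16, 74 and 71.04 give d = 0.507, 0.465 and 0.475.

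**2. Information kept by the cut.** Cutting a normal marker so that a fraction q is positive multiplies its correlation with the outcome by f = φ(z)/√(q(1−q)), where z is the cut. The information kept is f².
- q = 0.30: f = 0.3477/0.4583 = 0.759, f² = 0.576
- q = 0.50: f = 0.3989/0.5000 = 0.798, f² = 0.637
- q = 0.60: f = 0.3863/0.4899 = 0.789, f² = 0.622

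**3. Power when either test is anchored at 80%.** At 80% power the standardised effect is 1.960 + 0.842 = 2.802. The binary test's value is f times that of the continuous test.

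| q | Binary at 80%: continuous = Φ(2.802/f − 1.960) | Cost | Continuous at 80%: binary = Φ(2.802f − 1.960) | Cost |
|---|---|---|---|---|
| 0.30 | 95.8% | 15.8 | 56.6% | 23.4 |
| 0.50 | 94.0% | 14.0 | 60.8% | 19.2 |
| 0.60 | 94.4% | 14.4 | 59.8% | 20.2 |

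**4. Severity and LTCD at the protocol's own d, N = 148.** Binary power is Φ(d√(h/2) − 1.960). The implied continuous correlation is ρ = r/f, with r = d/√(d² + 1/(q(1−q))). Its power is Φ(atanh(ρ)·√145 − 1.960). For q = 0.30 and d = 0.55:
- Binary: 0.55 × √31.08 = 3.066, power 86.6%.
- Continuous: r = 0.244, ρ = 0.322, 0.334 × 12.04 = 4.02, power 98.0%. The cost is 11.5 points (from unrounded values).

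With d = 0.50 the result is 86.0% v 96.6% at q = 0.50 (10.5 points) and 84.6% v 96.3% at q = 0.60 (11.7 points).

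**5. H3b, 74 v 74.** Simulation with likelihood-ratio tests and 8,000 runs per row. Delirium cases are shifted by the stated number of SDs, and the odds ratio is the one seen after the cut.

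| Shift (SD) | Odds ratio, q 0.30–0.60 | Continuous power | Binary power | Cost in points |
|---|---|---|---|---|
| 0.45 | 2.05–2.11 | 0.79 | 0.55–0.62 | 17–24 |
| 0.55 | 2.41–2.50 | 0.92 | 0.72–0.78 | 14–19 |
| 0.62 | 2.70–2.81 | 0.96 | 0.81–0.87 | 10–15 |
| 0.70 | 3.07–3.22 | 0.99 | 0.89–0.93 | 6–10 |
| 0.80 | 3.62–3.83 | 1.00 | 0.95–0.98 | 2–5 |

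**The case against.** **The binary contrast has a rationale.** A.2.1 places all three aims of Project 1 under the ATN scheme, and H1a, H1b and H2b also use biomarker positivity. Aim 3 can be read as asking whether plasma abnormality behaves like CSF abnormality, so a per-SD slope partly changes the question. This stands. It would be wrong to infer that ATN covers only the CSF and PET aims, and it is a good reason to keep the binary result as a secondary analysis. It does not supply a plasma threshold, and it does not fit an aim stated in levels.

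**H3b coding is implied, not fixed.** A reader might infer that the protocol rules out any use of the continuous level. It does not say so. Only H3c names the binary exposure outright, and Table 6 lists ROC and predictive modelling for Project 1, which could use the level. The wording of H3b and its power text still point to abnormal v normal.

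**The missing plasma cut-point is not itself an error.** A statistical analysis plan would commonly hold it. It matters here only because no stated threshold argues for the cut.

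**The loss is not uniform.** A reader might infer 20 or more points throughout. That applies only to modest effects: at the protocol's own d it is about half that, and for large odds ratios it is small. The figures also reduce H3c's mixed model to a simple correlation and leave out the planned covariates.

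**Exploratory aim.** Nothing stated is wrong on this point, and the consequence is limited.

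**Conclusion.** The point holds as a cheap improvement, not as an error. For H3c explicitly, and for H3b by its wording and power text, the plan uses a two-level exposure for an aim stated in levels. Under a normal transformed marker and a linear effect, the cut keeps 58–64% of the information. The cost is:
- about 14–23 points of power with either test anchored at 80%;
- about 11–12 points at the protocol's d of 0.50–0.55 in 148 patients;
- about 17–24 points for H3b at an odds ratio near 2.1;
- about 10 points or fewer above an odds ratio of about 3.

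The protocol does not give the marker's distribution or the shape of its effect. All figures are unadjusted, and covariates would change the absolute power. A true threshold at the cut would shrink or remove the loss. Priority is low because the aim is exploratory.

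**What to change.** In B.2.3, Project 1, Aim 3 Analyses:
- Make the transformed plasma t-tau and NFL level, per SD, the main exposure for H3b (logistic and linear models) and for H3c (level by long-term time).
- Check linearity with a spline term, which would also show a threshold if there is one.
- Keep abnormal v normal as a secondary analysis, for comparability with the ATN-based CSF aims.

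In B.1.3, Project 1, Aim 3, restate the detectable effects per SD at N = 148. Unadjusted, and under the assumptions above, these are a correlation of about 0.23 for severity and LTCD. For delirium, a shift of 0.465 SD gives about 80% power, which is an odds ratio of exp(0.465) = 1.59 per within-group SD.

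The cost is wording only: no new samples, assays or visits. The downside is that the main effect is reported per SD and not for a positive patient; the secondary analysis covers that.
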